4.2.1 Primary

- The frequencies, intensities, and duration of solicited local AEs on Day 1 and Day 29 and the following 7 days by dose and group.
- The frequencies, intensities, duration, and relationship to trial vaccination of solicited systemic AEs on Day 1 and Day 29 and the following 7 days by dose and group.
- The occurrence, intensities and relationship to trial vaccination of unsolicited AEs on Day 1 and Day 29 and the following 28 days by dose and group.
- The occurrence and relationship to trial vaccination of SAEs and AESIs throughout the trial.

On Day 29 and Day 43:

- The proportion of subjects seroconverting for SARS-CoV-2 spike protein antibodies, as measured by ELISA.

- Individual SARS-CoV-2 spike protein-specific antibody levels in serum, as measured by ELISA.
- Geometric mean titers (GMTs) of serum SARS-CoV-2 spike protein antibodies, as measured by ELISA.
- The proportion of subjects seroconverting for SARS-CoV-2 neutralizing antibodies, as measured by an activity assay.
- Individual SARS-CoV-2 neutralizing antibody levels in serum.
- GMTs of serum SARS-CoV-2 neutralizing antibodies, as measured by an activity assay.

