7.3.2 Licensed/Authorized Vaccine

Since the efficacy results from Trial CV-NCOV-004 are available and all subjects in this trial are currently eligible to receive a licensed/authorized vaccine, all subjects in this trial will be unblinded.

Each subject will be informed by the study physician of the available efficacy results from Trial CV-NCOV-004 and whether he/she received CVnCoV or an active control. All subjects will be asked to remain in the trial to allow safety follow-up.

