### 9.4 Estimands

ENDPOINTS (subject level)	ESTIMANDS (population level)
Primary Safety	

The frequencies, intensities, and duration of solicited local AEs on Day 1 and Day 29 and the following 7 days by dose and group.
 
The frequencies, intensities, duration, and relationship to trial vaccination of solicited systemic AEs on Day 1 and Day 29 and the following 7 days by dose and group.
 
The occurrence, intensity and relationship to trial vaccination of unsolicited AEs on each vaccination day and the following 28 days by dose and group.
 
The occurrence and relationship to trial vaccination of SAEs and AESIs throughout the trial.
	
Safety set. Subjects who were unblinded and/or received an authorized/licensed COVID-19 vaccine will be censored at the day after unblinding and/or vaccination receipt.
 
The number and percentage of subjects overall and by dose level:
 
Each solicited local AE within 7 days after each trial vaccination by intensity and overall.
 
Each solicited systemic AE within 7 days after each trial vaccination by intensity, by relationship to trial vaccine and overall.
 
The mean duration in days by group with standard deviation of solicited AEs (within the solicited period, total duration).
 
At least 1 unsolicited AEs, at least 1 grade unsolicited AEs and each unsolicited AEs by SOC/PT occurring within 28 days after each trial vaccination and overall by causal relationship to trial vaccine and overall.
 
At least 1 SAE, or at least 1 AESI to vaccine overall by causal relationship to trial vaccine and overall.

ENDPOINTS (subject level)	ESTIMANDS (population level)
Primary Immunogenicity	

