## 10.8 Censoring Rules for Subjects Unblinded and/or Treated with Alternate Licensed/Authorized Vaccine

Since the efficacy results from Trial CV-NCOV-004 are available and all subjects in this trial are currently eligible to receive a licensed/authorized vaccine, all subjects in this trial will be unblinded following protocol version 3.0. Hence, all subjects will be unblinded prior end of the trial, and their data will be censored in all analyses. The below rules are still applicable as subjects could request unblinding or became eligible to receive a licensed/authorized vaccine prior to the protocol V3.0.

The following censoring rules will be applied to these subjects to avoid any study bias.

- Subjects who are unblinded will be censored for the safety endpoints at the first day after unblinding. Any related follow-up data that is collected from censoring time point forward will be included in the listings output.
- Subjects who are unblinded but decide not to receive the alternate licensed/authorized vaccine and to stay in the study will be analyzed for immunogenicity as planned.
- Subjects who are unblinded, but decide to receive the alternate licensed/authorized vaccine, will have their immunogenicity data censored at the first day after receiving the alternate licensed/authorized vaccine. However, any related follow-up data that is collected from this time point forward will be included in the listings output.
- Subjects who received an alternate licensed/authorized vaccine without or before being unblinded will be censored for safety and immunogenicity at the first day after receiving the alternate licensed/authorized vaccine. As described above, data collected from the censoring timepoint forward will be included in the listings output.

This is summarized in Table 7.

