**Table 7 Censoring Rules for Subjects Unblinded Prior to Protocol Version 3.0**

Analysis	Treatment Received in CV-NCOV-002	Alternate Licensed/Authorized Vaccine Received?	Censoring Rule
Safety	CVnCoV	No Yes	Censored at the first day after unblinding
	Active Control	No Yes	
Immunogenicity	CVnCoV	No	Analyzed as planned
		Yes	Censored at the first day after receiving the alternate licensed/authorized vaccine.
	Active Control	No	Analyzed as planned
		Yes	Censored at the first day after receiving the alternate licensed/authorized vaccine

The following details are to be followed regarding censoring the day after unblinding:

- Unblinding day ( = Pacific Time Zone) must be adjusted to the subject's time zone.
- Unblinding time does not matter for anything apart from the above time zone normalization. (As case start time is not collected.)
- If the case start day and the unblinding day occur on the same day the case will count for the analysis. (Censoring starts at the day after the unblinding.)

The following details are to be followed regarding censoring the day after receiving the alternate licensed/authorized vaccine:

- Times are not relevant as neither alternate licensed/authorized vaccine time nor case start time are collected.
- If alternate licensed/authorized vaccine date is complete then censoring starts at first day after the alternate licensed/authorized vaccine day.
- If alternate licensed/authorized vaccine date is incomplete (only day missing) then censoring starts after this month.
- If alternate licensed/authorized vaccine date is incomplete (month missing, year available) then censoring starts after this year.
- If alternate licensed/authorized vaccine date is completely missing then no censoring can be made.

As these imputations of incomplete licensed vaccine dates are not an ideal solution this is only to be considered as a fallback solution in case complete licensed vaccine dates cannot be retrieved and an interim workaround for unclean data during study conduct.

All incomplete or missing licensed vaccine dates need to be queried.

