## 12.8 Adverse Events

The primary, secondary and exploratory endpoints will be analyzed overall, as well as in subjects retrospectively SARS-CoV-2 seronegative at baseline, and in subjects retrospectively SARS-CoV-2 seropositive at baseline as per the definition given in section 10.6.3.

Unsolicited AEs, including SAEs, and AESIs and solicited AE integrated to or recorded on the CRF will be coded using MedDRA Version 24.0 or higher, by SOC and PT.

If not stated otherwise, all summaries of unsolicited AEs will also include relevant solicited AEs.

For outputs presenting occurrence of AEs for a defined period after a dose, the following distinctions are made if not otherwise stated; by any dose, dose 1, dose 2 and booster at day 57 and day 180. Any dose is defined as a subject who received at least one dose of either CVnCoV or active control.

In general, percentages will be based on the number of subjects in the respective analysis set. In summary tables for AEs after the second or booster vaccination, percentages will be based on the number of subjects in the respective analysis set who received the second, or booster vaccination as applicable.

The primary and secondary safety endpoints will be analyzed using the safety set.

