A listing of all SAEs will further be provided by subject, including both unsolicited and solicited AEs.

---

Further AE listings supporting the AE tables described above will include both relevant solicited and unsolicited AEs. Solicited AEs occurring on the day of vaccination and the following 7 days and unsolicited AEs will be listed together.

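### The SAP's primary safety estimand stops counting SAEs and AESIs the day after unblinding, although the protocol endpoint runs to the end of the trial; the rule is not reconciled with SAP 12.8.1

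*SAP*

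**What the plan says.** Protocol 4.2.1 lists as a primary endpoint: "The occurrence and relationship to trial vaccination of SAEs and AESIs throughout the trial". Protocol 10.3.5.1 repeats it, and 5.5 plans at least 365 days of safety follow-up after the last primary dose. Protocol 7.3.2 unblinds everyone and adds: "All subjects will be asked to remain in the trial to allow safety follow-up". I found no safety censoring rule in the protocol.

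The SAP does have one, stated in two places with different scope:

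- **SAP 9.4, primary safety estimand.** Beside the same whole-trial endpoint: "Subjects who were unblinded and/or received an authorized/licensed COVID-19 vaccine will be censored at the day after unblinding and/or vaccination receipt". It is not limited by protocol version and makes no exception for subjects who took no other vaccine.
- **SAP 10.8.** "Subjects who are unblinded will be censored for the safety endpoints at the first day after unblinding", followed by "Any related follow-up data that is collected from censoring time point forward will be included in the listings output". The text introduces these rules as still needed for subjects unblinded or vaccine-eligible before version 3.0, and Table 7 is titled "Censoring Rules for Subjects Unblinded Prior to Protocol Version 3.0". For safety, Table 7 gives one rule whether or not another vaccine was received. The section also says that all subjects will be unblinded before the trial ends and that their data are censored across the board, without naming a day.

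On reporting, SAP 12.8 says: "In general, percentages will be based on the number of subjects in the respective analysis set". SAP 12.8.1 promises SAE and AESI tables for all reported AEs, including those more than 28 days after any dose, and: "A listing of all SAEs will further be provided by subject, including both unsolicited and solicited AEs". SAP 6.1, which lists changes from the protocol, names only the listing of CMI data and the asymptomatic-infection summary.

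**The concern.** Follow-up is collected for a primary endpoint and then, on the likelier reading, left out of that endpoint's tables. Late SAEs and AESIs, such as potential immune-mediated diseases, are a main purpose of the long follow-up. An event after unblinding would appear in a listing but not in the count or percentage by dose and age. Someone who reads only the tables could take an uncounted event for an absent one.

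The rule also goes further than its most natural motive. Stopping at a licensed vaccine separates CVnCoV events from events that may belong to another product. Stopping at unblinding removes follow-up from subjects who took no other product.

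**Working it through.** The plan gives no figure for this loss, so there is nothing to reproduce. The check has two parts.

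**1. Direction.** Let N be the number of subjects in the analysis set, U a subject's unblinding day and E the last day of follow-up.

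- Protocol endpoint: 100 × (subjects with an event up to E) / N.
- Censored table: 100 × (subjects with an event up to U) / N.

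By SAP 12.8, N is not reduced for censoring, and the SAP specifies no subject-time rate or time-to-event method for AEs. Subjects with an event up to U are a subset of those with an event up to E. The censored percentage is therefore at most the protocol percentage, and equal only if no subject has a first event after unblinding.

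**2. Size, as an illustration only.**

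Inputs from the documents:
- The final contact is nominally Day 393, anchored on Day 180 (window ±10 days), with its own window of 0 to +30 days (protocol Table 1). E is therefore 393, with a range of 383 to 433.
- Protocol version 3.0 is dated 3 December 2021 (protocol Appendix 12).

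Assumptions: unblinding on 3 December 2021, and the first-dose dates in the table.

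Formula: share of follow-up lost = (E − U) / E, or zero if U is at or after E.

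First-dose date with no loss: 3 December 2021 minus 392 days = 6 November 2020. Over the windows it is 16 November 2020 (E = 383) to 27 September 2020 (E = 433).

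| Assumed first dose | U on 3 Dec 2021 | Lost, E = 393 | Lost, E = 383 to 433 |
|---|---|---|---|
| 1 Dec 2020 | 368 | 25/393 = 6.4% | 3.9% to 15.0% |
| 1 Jan 2021 | 337 | 56/393 = 14.2% | 12.0% to 22.2% |
| 1 Feb 2021 | 306 | 87/393 = 22.1% | 20.1% to 29.3% |

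Later implementation at sites shrinks these shares. Earlier unblinding on request enlarges them: an assumed U of 270 loses 123/393 = 31%, and 180 loses 213/393 = 54%.

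Effect on the percentage, assuming a constant hazard and whole-trial risk r: tabulated risk = 1 − (1 − r)^(1 − share lost). The documents give no SAE or AESI rate, so r is shown over a range.

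| Assumed r | 6.4% lost | 14.2% lost | 22.1% lost |
|---|---|---|---|
| 1% | 0.94% | 0.86% | 0.78% |
| 2% | 1.87% | 1.72% | 1.56% |
| 5% | 4.69% | 4.30% | 3.92% |

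Each cell treats all subjects as sharing one first-dose date, which real enrolment will not do.

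The 7-day and 28-day AE windows are not touched in these scenarios. The window after dose 2 closes at Day 29 + 28 = 57 and after the later booster at Day 180 + 28 = 208, both before Day 306. The exposed part is the long-term SAE/AESI endpoint.

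**The case against.** **Late events may be tabulated after all.** SAP 12.8.1 commits to SAE and AESI tables for all reported AEs beyond 28 days. This stands in part: a reader might infer that post-unblinding events appear in listings only, and the documents do not settle that. But 12.8.1 states no exemption from censoring, while 9.4 attaches the rule to this very endpoint.

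**The timed rule in 10.8 covers only unblinding before version 3.0.** This is right for the bullets and Table 7, which cannot by themselves be read as covering everyone. The general rule with a time point is the one in 9.4.

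**The rule is disclosed and has a reason.** It appears in 9.4, 10.8 and the SAP change history. A reader might infer a concealed change; the documents do not support that, and the omission from 6.1 is a documentation gap. The SAP says the aim is to avoid bias, the trial is descriptive, and the protocol leaves methodology to the SAP. For a licensed vaccine the reason is sound. It is weaker for unblinding alone. The sponsor and safety committees were already unblinded (SAP 8.7), and AEs after up to 30 + 30 + 30 = 90 open-label booster doses are tabulated as a secondary endpoint.

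**The cases are not lost.** True: every SAE is listed by subject, and post-censoring data are listed. SAP 12.3 adds a separate summary table for unblinded or censored subjects, but it sits under demographics and its contents are not specified. Listings keep the cases but give no rate by dose or age.

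**Conclusion.** The point holds and should be fixed. As 9.4 is written, the primary SAE/AESI estimand ends the day after unblinding, short of the protocol endpoint, and the error can run only one way. Whether 12.8.1 restores the later events is unresolved, with exclusion the likelier reading.

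The size is unknown and may be zero. A reader might infer a large loss for all subjects, but the documents give no dosing or unblinding dates. The 6%, 14% and 22% rest wholly on the assumed dates. For Groups 1 and 2 there is a hint of little or no loss. The protocol amendment entry of 20 October 2020 describes them as already randomized. If dosing followed promptly, a first dose on that date reaches Day 393 on 16 November 2021, before version 3.0; only the late visit windows would leave some follow-up exposed.

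A reader might also see the solicited-only Grade 3 composite in SAP 12.8.2 as a second instance. It is not: the label states the restriction, related SAEs stay in, and related Grade 3 unsolicited AEs have their own row in 12.8.1.

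**What to change.** - **SAP 9.4, 10.8 and 12.8.1:** state that SAEs, AESIs and AEs leading to withdrawal are tabulated over all follow-up, split before and after unblinding and before and after a licensed vaccine, with subject-time at risk in each part.
- Keep the censored tables alongside, and say which tables the censoring rule governs, so that 12.8.1 has one reading.
- **SAP 6.1:** record the censoring of the primary safety endpoint as a departure from the protocol.
- **SAP 10.8:** align the sentence that censors all subjects' data in every analysis with the immunogenicity rule. That rule analyzes unblinded subjects as planned unless they receive a licensed vaccine.

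The cost is SAP wording and one extra set of tables; no new data are needed. The drawback is that post-unblinding data are open-label and partly follow another vaccine, which the split makes visible.

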5 TRIAL DESIGN

5.1 Overall Design

This is a Phase 2a, partially blind, active-controlled, dose-confirmation trial to assess the safety and immunogenicity of provisionally selected CVnCoV dose levels of 6 and 12 µg in an older adult population. The design of the trial will allow an increase or decrease in dose based on data from Trial CV-NCOV-001 and this trial (see Section 5.2). An overview of the planned number of subjects to be enrolled per trial group and the vaccination schedule is provided in Table 2.

Subjects will be recruited independent of their SARS-CoV-2 serology status. Their serostatus will be determined retrospectively by a blood sample drawn at baseline and analyzed to allow post hoc stratified analyses of subjects who are SARS-CoV-2 seronegative or seropositive at baseline.

In the initial phase, subjects will be enrolled in 3 cohorts divided into 6 groups:

- 6 µg dose level cohorts
 - Group 1 (observer-blind): CVnCoV 6 µg on Day 1 and 6 µg on Day 29 (in subjects 18 to 60 years of age)
 - Group 2 (observer-blind): CVnCoV 6 µg on Day 1 and 6 µg on Day 29 (in subjects >60 years of age [i.e., 61 years or older])
- 12 µg dose level cohorts
 - Group 3 (observer-blind): CVnCoV 12 µg on Day 1 and 12 µg on Day 29 (in subjects 18 to 60 years of age)
 - Group 4 (observer-blind): CVnCoV 12 µg on Day 1 and 12 µg on Day 29 (in subjects >60 years of age [i.e., 61 years or older])
- Active control cohort
 - Group 5 (observer-blind): licensed hepatitis A vaccine on Day 1 and on Day 29 (in subjects 18 to 60 years of age)
 - Group 6 (observer-blind): licensed pneumococcal vaccine on Day 1 and on Day 29 (in subjects >60 years of age [i.e., 61 years or older])

A subgroup of subjects in Group 3 will receive a booster dose of CVnCoV on Day 180 and a subgroup of subjects in Group 4 will receive a booster dose of CVnCoV on Day 57 or Day 180, each in an open-label manner.

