	Safety set. Applicable for subjects who received a booster dose at day 57 or day 180. Subjects unblinded and/or received an authorized/ licensed vaccine during the course of the trial will be censored at the day after unblinding or receipt of authorized/ licensed vaccine (whichever is earlier).

ENDPOINTS (subject level)	ESTIMANDS (population level)

 
The frequencies, intensities, and duration of solicited local AEs on the day of the booster administration and the following 7 days by group.
 
The frequencies, intensities, duration, and relationship to trial vaccination of solicited systemic AEs on the day of the booster administration and the following 7 days by group.
 
The occurrence, intensities and relationship to trial vaccination of unsolicited AEs on the day of the booster administration and the following 28 days by group.
 
	
The number and percentage of subjects by group reporting:
 
 
Each solicited local AE within 7 days after each trial booster vaccination by intensity and overall
 
Each solicited systemic AE within 7 days after each trial booster vaccination by intensity, by relationship to trial vaccine and overall.
 
At least 1 unsolicited AEs, at least 1 grade 3 unsolicited AEs and each unsolicited AEs by SOC/PT occurring within 28 days after each trial booster vaccination and overall by causal relationship to trial vaccine and overall
 
The mean duration in days by group with standard deviation of solicited AEs (within the solicited period, total duration).
 

Secondary Immunogenicity	

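### Booster adverse-event endpoints are censored at formal unblinding although the booster is open-label with no control booster, so boosted subjects unblinded before or during the window can be counted as event-free

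*SAP*

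**What the plan says.** The Secondary Safety row of the table in SAP 9.4 is confined to boosted subjects: "Applicable for subjects who received a booster dose at day 57 or day 180". It then says: "Subjects unblinded and/or received an authorized/ licensed vaccine during the course of the trial will be censored at the day after unblinding", or after the other vaccine if that comes first. SAP 10.8 gives the general rule, "Subjects who are unblinded will be censored for the safety endpoints at the first day after unblinding", with no exception for the booster. The only reason offered is this: "The following censoring rules will be applied to these subjects to avoid any study bias". Safety data from after the cut-off appear in listings only.

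Immunogenicity is treated differently. Under SAP 10.8, a subject who is unblinded, declines the alternative vaccine and stays in the trial "will be analyzed for immunogenicity as planned".

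Protocol 5.1 gives the boosters "on Day 57 or Day 180, each in an open-label manner". Protocol Table 2 and SAP Table 1 show three booster subgroups of 30 (Group 3 at Day 180, Group 4 at Day 57, Group 4 at Day 180) and no booster in any control group. For tables after the booster, SAP 12.8 takes as denominator the subjects in the analysis set who received that booster.

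**The concern.** Censoring at unblinding makes sense where knowledge of allocation could distort a comparison between blinded arms. For the booster endpoints there is no such comparison: subject and site know that CVnCoV was given, and there is no control booster. The unblinding trigger therefore removes data without protecting a blinded contrast, and the SAP does not name any other bias that it has in mind.

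Two consequences follow. The two secondary objectives, booster safety and booster immunogenicity, treat the same unblinded subject differently. More importantly, the events leave the numerator while the subject stays in the denominator, so the tabulated reaction rates can only move downwards. For a safety objective that is the unfavourable direction.

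**Working it through.** **Check of the interval method.** The documents give no figure for booster safety or for the effect of censoring. The beta interval of SAP 10.5.10 does reproduce the plan's own sample-size table: 72 of 90 with a Beta(1.9, 0.1) prior gives 80.3% (71.7 to 87.7), as in SAP Table 3.

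**What is lost, and when.**
- The solicited window is the booster day plus 7 days (8 days). The unsolicited window is the booster day plus 28 days (29 days).
- If unblinding comes before the booster, both windows are censored in full. If it falls inside a window, the days after it are censored. If it comes after the window, nothing in that window is lost.

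**Who could be affected.**
- Subjects unblinded individually before protocol version 3.0. SAP 8.7 allows a request from those eligible for a licensed vaccine, and SAP 10.8 provides for those who then decline it and stay. Protocol 7.3.1 also allows a subject to continue after emergency unblinding.
- Subjects unblinded under version 3.0, dated 03 December 2021, taking that date as the earliest possible. Day 180 falls 179 days after Day 1:
  - Solicited window: 179 + 7 = 186 days, so only subjects first dosed after 31 May 2021 are touched. With the +10-day visit window this is 196 days, or after 21 May 2021.
  - Unsolicited window: 179 + 28 = 207 days, or after 10 May 2021. With the visit window this is 217 days, or after 30 April 2021.
- Enrolment dates and numbers unblinded are not given, so neither group can be counted.

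**Effect on a tabulated rate.** Let p be the true rate and c the share of the subgroup unblinded before the booster. Assume that unblinding is unrelated to the risk of a reaction. Events are lost from the numerator only, so

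expected tabulated rate = p × (1 − c).

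The interval planned in SAP 12.8.2 for Grade 3 reactions or related SAEs uses a Beta(0.5, 0.5) prior, with limits at the 2.5% and 97.5% points of Beta(x + 0.5, n − x + 0.5). Take n = 30 (SAP Table 1) and assume p = 20%:

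| Assumed c | Expected rate | Example count | 95% interval |
|---|---|---|---|
| 0% | 20% | 6/30 = 20% | 8.8 to 36.7 |
| 10% | 20% × 0.90 = 18% | | |
| 25% | 20% × 0.75 = 15% | | |
| 50% | 20% × 0.50 = 10% | 3/30 = 10% | 2.9 to 24.3 |

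The values of p and c are assumptions. They show the mechanism and are not estimates for this trial.

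**The case against.** The strongest reply is that the rule may touch almost nobody. An individually unblinded subject must have declined the licensed vaccine, stayed in, and still been boosted. General unblinding came only with version 3.0, and SAP 11.1 reports that a booster interim analysis to Day 208 had already been performed. This stands: the realised loss cannot be shown to be large. It does not repair the rule, which still governs the final tables.

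A second reply is that some bias may be avoided after all. Under SAP 8.8 the version 3.0 disclosure also tells subjects the CV-NCOV-004 efficacy results, which could colour subjective reports even in an open-label group. Boosted subjects also feed trial-long tables set beside active control, where a single cut-off is defensible. Both points stand and limit the fix. Neither justifies counting a boosted subject as event-free.

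Third, post-censoring data remain in listings, SAP 12.3 plans a separate summary of unblinded or censored subjects, and all analysis is descriptive. These soften the problem but leave the booster percentages as they are.

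A reader might go further and infer that giving the open-label booster is itself the unblinding, so that nearly the whole window is lost for every boosted subject. The documents do not support this. SAP 10.8 ties censoring to a recorded unblinding day adjusted for time zone. Protocol 7.3.1, SAP 8.7 and SAP 8.8 describe unblinding as a code break, a subject's request or the version 3.0 disclosure. SAP 12.8 also plans full post-booster output that this reading would nearly empty.

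A reader might also infer that the booster sample shrinks and the intervals merely widen. SAP 12.8 keeps all boosted subjects in the denominator, so the effect is a diluted rate.

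**Conclusion.** The point holds as a defect in the rule, of unknown and possibly nil effect in practice. For the booster endpoints, censoring at formal unblinding protects no blinded comparison. Combined with the SAP 12.8 denominator, taken as written, it lowers reaction rates in proportion to the share of boosted subjects unblinded before the booster. In the illustration a true 20% becomes about 15% if a quarter were unblinded beforehand and 10% if half were. It is unchanged if none were. Unblinding part-way through a window has a smaller effect, limited to events after that day.

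The conclusion concerns the unblinding trigger only. Censoring at receipt of a licensed or authorized vaccine removes a real confounder and is not in question.

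**What to change.** - In SAP 9.4 (Secondary Safety) and SAP 10.8, state that the booster solicited endpoints (booster day plus 7 days) and unsolicited endpoints (booster day plus 28 days) are censored only at receipt of a licensed or authorized vaccine, not at unblinding.
- Keep the unblinding rule for the observer-blind primary-dose comparison and for the trial-long SAE and AESI tables set against active control.
- In SAP 12.8, base booster percentages on boosted subjects not censored before the window.
- Report, for each booster subgroup, the number of subjects censored within the window.

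The cost is a few sentences, a changed censoring flag and one added count. No new data are needed, because the events are already collected and listed. The one downside is small: reports made after a subject has learned the CV-NCOV-004 efficacy results would remain in the booster tables.
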